5. STUDY ENDPOINTS

5.A. Primary Endpoints

1. Evidence and nature of toxicity related to the treatment.
2. Evidence of response based on “median time to new metastasis” (See **Section 12.D.1**).

5.B. Secondary Endpoints

1. Persistence of transferred T cells in blood and in tumor (Group 2).
2. Functional capacity of transferred T cells (Group 2) (Please see **Section 12.E.3**).
3. Evidence of epitope spreading (See **Section 12.F**).

4. Disease response by RECIST criteria, and MCC-specific survival (See **Section 12.D.2**).

6. STUDY DESIGN

The proposed study is a Phase I/II trial aimed at treating 20 individuals with metastatic MCC.

Group 1: Due to the availability of the anti-PD-L1 antibody, ten patients with metastatic MCC who do not have an HLA type for which T cells can be generated (for example, who DO NOT express HLA A*0201, HLA A*2402 or HLA B*3502) or for whom T cells cannot be generated for technical issues, will be treated on Group 1 (

Figure 13). They will be planned to receive the anti-PD-L1 antibody as an infusion every 2 weeks for 12 months and an MHC class I up-regulation intervention (either localized radiation or an intra-tumor injection of 3.3×10^6 IU of IFN β -1B) between 7 and 10 days after the preceding infusion of anti-PD-L1 (or 7 to 4 days before the next anti-PD-L1). Patients may receive preferably one, but up to 3 infusions of anti-PD-L1 before the first MHC class I up-regulation intervention. Depending on the continued presence of detectable metastatic disease and if they remain clinically eligible, patients could undergo MHC class I up-regulation during the time anti-PD-L1 infusions were ongoing starting within four weeks of the preceding restaging scans.

Group 2: Ten patients with metastatic MCC who have an HLA type for which T cells can be generated (for example, who express HLA A*0201, HLA A*2402 and/or HLA B*3502) will be treated on Group 2. They will be planned to receive an infusion of anti-PD-L1 antibody every 2 weeks for 12 months, an MHC class I up-regulation intervention (either localized radiation or an intra-tumor injection of 3.3×10^6 IU of IFN β -1B) between 7 and 10 days after the first infusion of anti-PD-L1 and 2 to 5 days prior to receiving a first of 2 infusions (approximately 28 days apart) of no greater than 10^{10} cells/m 2 of polyclonal autologous MCPyV TAg-specific CD8 $^+$ T cells. For example, a patient with a surface area of 2 m 2 would receive no greater than 2×10^{10} total polyclonal autologous MCPyV TAg-specific CD8 $^+$ T cells. Restaging studies were performed 8 weeks after the first interventions to induce local MHC Class I upregulation. Similar for patients in Group 1, they may receive preferably one, but up to 3 infusions of anti-PD-L1 before the first MHC class I up-regulation intervention. A second attempt will be made to generate MCPyV TAg-specific CD8 $^+$ T cells if the initial cell production was unsuccessful and the final cell product will be infused as soon as it becomes available.

If patient has disease progression while on Group 1 alone, treatment may be stopped/interrupted to allow for disease control with other anti-cancer therapies. If T cells are generated and made available in the interim, the patient may resume therapy on Group 2 as long as eligibility criteria are met.

For safety considerations, low-dose SC IL-2 will not be administered after the T-cell infusions due to concurrent anti-PD-L1 treatment. Restaging studies will be performed 8 weeks after interventions to induce local MHC Class I upregulation by tumor tissue. Depending on the continued presence of detectable metastatic disease and if the patient

remains clinically eligible, patients could undergo the same treatment (MHC class I up-regulation, two CTL infusions approximately 28 days apart) during the time anti-PD-L1 infusions were ongoing starting within four weeks of the preceding restaging scans.

[figure not shown]

Figure 13. Study decision tree (Groups 1 and 2)

7. ELIGIBILITY FOR TREATMENT

7.A. Inclusion Criteria

1. Signed written informed consent.
2. Confirmation of MCC by internal pathology review of initial or subsequent biopsy or other pathologic material.
3. If an accessible lesion is present, a biopsy will be performed within 6 weeks of the start of study intervention. The results of the biopsy must be obtained prior to initiation of study intervention.
4. Evidence of MCPyV TAg tumor expression by immunohistochemistry on any prior or current tumor specimen or viral oncoprotein antibody confirmation within 6 weeks of the start of study intervention.
5. ECOG PS ≤ 2 at trial entry.
6. 18 years of age or older.
7. Patients must have at least one bi-dimensionally measurable lesion by palpation, clinical exam, or radiographic imaging within 6 weeks of the start of study intervention (X-ray, CT scan, PET scan, MRI, or Ultrasound).
8. For patients designated to be treated on Group 2: cardiac ejection fraction ≥35%. For patients with significant risk factors for coronary artery disease (Framingham risk score > 15%), a cardiac stress test is recommended.
9. At least 3 weeks must have passed since any of the following: systemic corticosteroids, immunotherapy (for example, T-cell infusions, immunomodulatory agents, interleukins, MCC vaccines, intravenous immunoglobulin, expanded polyclonal TIL or LAK therapy), pentoxifylline, other small molecule or chemotherapy cancer treatment, other investigational agents **or other systemic agents that target Merkel cell carcinoma.**

7.B. Exclusion Criteria

1. Known active infections or oral temperature >38.2 C fewer than 72 hours prior to receiving study treatment or systemic infection requiring chronic maintenance or suppressive therapy.
2. CBC profile prior to trial entry:

WBC < 2000/mcl
Hb < 8 g/dL
ANC < 1000/mcl
Platelets < 50,000/mcl

3. New York Heart Association functional class III-IV heart failure, symptomatic pericardial effusion, stable or unstable angina, symptoms of coronary artery disease, congestive heart failure, clinically significant hypotension, or history of an ejection fraction of $\leq 30\%$ (echocardiogram or MUGA).
4. Clinically significant pulmonary dysfunction, as determined by medical history and physical exam. Patients so identified will undergo pulmonary functions testing and those with FEV1 < 2.0 L or DLco (corr for Hgb) < 50% will be excluded.
5. Creatinine clearance < 30 ml/min which cannot be attributed to MCC metastasis.
6. Total bilirubin > 1.5 x ULN, AST/ALT > 2.5 x ULN. For patients with liver metastases, AST/ALT > 5x ULN
7. Active autoimmune disease (e.g. systemic lupus erythematosus, vasculitis, infiltrating lung disease, inflammatory bowel disease) whose possible progression during treatment would be considered unacceptable by the investigators.
8. Symptomatic and untreated central nervous system (CNS) metastasis. However, patients with 1 to 2 asymptomatic, less than 1 cm brain/CNS metastases without significant edema may be considered for treatment. If sub-centimeter CNS lesions are noted at study entry, then repeat imaging will be performed, if more than 4 weeks have elapsed from the last scan.
9. Any condition or organ toxicity that is deemed by the PI or the attending physician to place the patient at unacceptable risk for treatment on the protocol.
10. Pregnant women, nursing mothers, men or women of reproductive ability who are unwilling to use effective contraception or abstinence. Women of childbearing potential must have a negative pregnancy test within 2 - 6 weeks prior to treatment.
11. Clinically significant and ongoing immune suppression including, but not limited to, systemic immunosuppressive agents such as cyclosporine or corticosteroids, CLL, uncontrolled HIV infection, or solid organ transplantation.
12. Patients may not be on any other treatments for their cancer aside from those included in the protocol. Patients may not undergo another form of treatment concurrently with this study.

13. Known severe hypersensitivity reactions to monoclonal antibodies (Grade ≥ 3 NCI-CTCAE v 4.0), any history of anaphylaxis, or uncontrolled asthma.
14. Vaccination with live inactivated viral strains for the prevention of infectious diseases within 4 weeks of the start of the study treatment. Inactivated influenza vaccines are permitted while on trial.
15. Known alcohol or drug abuse.
16. Legal incapacity or limited legal capacity.

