12. EVALUATION

See **Protocol Appendix B** for a summary of patient evaluation for Groups 1 and 2. The dates listed on the study calendar are approximate as many patients reside out of the area and may not always follow the time points as dictated by the protocol. Results of tests and, or procedures conducted as standard of care may be used for research purposes. Potential patients will initially be identified and recruited through the SCCA MCC clinic. The informed consent form will be discussed and signed in the presence of a GCP-trained investigator. Patients who are found eligible to participate in this protocol will be followed closely by a multidisciplinary oncology team that includes medical oncologists, dermatologists and radiation oncologists (as appropriate).

12.A. Patient Evaluation at Each Planned Visit

Patients will have a history taken, ECOG performance status (Appendix A), a physical exam with vital signs prior to the T-cell infusion and 1, 14, and 28 days after each infusion. Thyroxine 3 (T3), free thyroxine 4 (FT4) and thyroid stimulating hormone (TSH) at baseline, at cycle 6 and then every 6 cycles. Merkel virus oncoprotein serology at baseline and at time of radiographic evaluation. A comprehensive chemistry panel, and a complete blood count at each planned visit including the pre-treatment visit, prior to Avelumab infusion, prior to IFN β -IB injections or radiation, prior to tissue biopsy or aspiration, prior to the T-cell infusion and 1, 3, 7, 14, and 28 days after each T cell infusion (Appendix B). It is anticipated that some patients reside outside of the area and

may have their +7, +14 and +28 day clinical evaluations completed locally (visits can occur +/- 1 day, weekly visits can occur +/- 3 days before or after the planned date).

12.B. Patient Evaluation During T-Cell Infusions

Blood pressure, heart rate, temperature, respiratory rate, and O₂ saturation (by pulse oximetry) will be recorded at time 0, every 15 minutes during the 1 to 2 hour T-cell infusion, end of infusion, hourly for 2 hours following the T-cell infusion. Adverse events will be managed by standard medical practice (see also **Section 13**).

12.C. Clinical and Laboratory Evaluation for Toxicity (General Toxicity Assessment)

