The period of monitoring for treatment-related toxicity will start with the first Avelumab infusion. All grade ≥ 3 CTCAE v.4.03 AEs will be recorded up to the last T cell or avelumab infusion. Beginning 4 weeks after the last study infusion, only study related toxicities will be collected per section 15. To evaluate for potential toxicities, patients will undergo a history and physical and, or laboratory evaluations (comprehensive chemistry panel and complete blood count) immediately prior to Avelumab infusion, prior to radiation therapy or intralesional IFN β -1B injection, immediately prior to infusions, days +1, +3, +7, +14, and +28 after each T cell infusion, and then as clinically indicated after the last infusion (for example, every 3 months for the first year, every 6 months for a year and then yearly see **Appendix B**). Clinical assessments at days +7, +14 and +28 after T-cell infusions may be performed by the patient's local provider and records assessed by the investigator within 14 days for any toxicities not previously assessed.

12.D. Efficacy Assessment

12.D.1. Clinical response by 'median time to new metastasis' (primary endpoint)

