- Growth factors (granulocyte colony stimulating factor or granulocyte macrophage colony stimulating factor). Exception: erythropoietin and darbepoietin alpha may be prescribed at the Investigator's discretion
- Bisphosphonate treatment is not allowed unless it has been initiated more than 14 days prior to receiving the first administration of Avelumab

13.G. Off-study Criteria

A patient's participation on the protocol will be terminated for any of the reasons listed below:

- Progressive disease or development of new metastasis requiring urgent additional drugs (for example chemotherapy)
- The participant withdraws consent
- Patient death
- Occurrence of pregnancy
- Participation in another trial during the treatment duration of this trial
- Occurrence of an exclusion criterion, which is clinically relevant and affects the subject's safety, if discontinuation is considered necessary by the Investigator or Sponsor
- A patient will no longer be eligible to receive additional therapy if the PI or his designee determines that additional T cell and / or avelumab infusions are not in the best interest of the patient
- Occurrence of any non-pre-existing AEs / repetitive Grade 2 AEDRs that are deemed related to the treatment as defined in **Section 13.C.2.**

- Use of a non-permitted concomitant drug such as steroids, or as defined in **Section 13.F.4** for which the predefined consequence is withdrawal from the trial
- The reasons for premature discontinuation must be recorded on the case report form. The patient may re-enter the study after premature discontinuation only by approval of the PI

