APPENDIX B

Group 1 Monitoring Schedule^a

GROUP 1		Event	History and PE	Chemistry Panel	CBC	T3 FT4 TSH	Tumor Biopsy	Blood for Research	Radiographic Evaluation	Oncoprotein Serology
Pre-treatment		Evaluation for treatment	X	X	X	X ^f	X ^g	X	X ^b	X
	Day 0	PD-L1 infusion ^c	X	X	X			X		
Week +1/+2	Day +7 - +10	Administer Radiation OR Intralesional IFNβ-1B	X	X	X			X		
Week +2	Day +14	PD-L1 infusion	X	X	X			X		
Week +4	Day +28	PD-L1 infusion	X	X	X		X ^g	X		
Week +6	Day +42	PD-L1 infusion	X	X	X			X		
Week +8	Day +56	PD-L1 infusion	X	X	X			X		
Week +9	Day +63	Staging							X (Day 56-70)	X
Week +10	Day +70	PD-L1 infusion	X	X	X	X ^f		X		
Week +11/+12	Day +77- +80	Administer Radiation OR Intralesional IFNβ-1B (if indicated) ^d	(X)	(X)	(X)			(X)		
Week +12	Day +84	PD-L1 infusion	X	X	X			X		
Week +14	Day +98	PD-L1 infusion	X	X	X			X		
Week +16	Day +112	PD-L1 infusion	X	X	X			X		
Week +18	Day 126	PD-L1 infusion	X	X	X			X		
Week +19	Day +133	Staging							X (Day 126-140)	X
Week +20	Day +140	PD-L1 infusion	X	X	X			X		
Week +22	Day +154	PD-L1 infusion	X	X	X	X ^f		X		
Week +24	Day +168	PD-L1 infusion	X	X	X			X		
Beyond +52 weeks		Study ends	X ^e	X ^e	X ^e			X ^e	X ^e	X
Beyond +24 weeks infusion Q2 weeks for up to 1 year total on treatment		PD-L1 infusion	X	X	X			X		

Test results and procedures conducted as per standard of care may be used for eligibility determination and evaluation for toxicity.

^a The dates listed on the study calendar above are approximate as many patients are expected to reside out of state and his oncologists and laboratories may not always be able to follow the time points as dictated by the protocol.

^b Includes brain evaluation.

^c Patients may receive preferably one, but up to 3 infusions of anti-PD-L1 before the first MHC class I up-regulation intervention.

^d The MHC class I upregulation can be repeated once, at any time point, if there is radiological disease present.

Treatment must start within 4 weeks of the preceding radiological evaluation.

^e At least every 3 months for one year, every 6 months for one year then yearly and as clinically indicated.

^f at baseline, at cycle 6 and then every 6 cycles.

^gIf accessible.

Group 2 Monitoring Schedule^a

GROUP 2		Event	History and PE	Chemistry	CBC	T3 FT4 TSH	Tumor Biopsy	Blood for Research	Radiographic Evaluation	Oncoprotein Serology
Pre-treatment	Evaluation for treatment	X	X	X	X	X ^f	X ^g	X	X ^b	X
	Day 0	PD-L1 infusion ^c	X	X	X			X		

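### The eligibility rule accepts a negative pregnancy test up to 42 days old at the first avelumab infusion, and no later test is called for in the text available

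*Combined protocol and SAP*

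**What the plan says.** Section 7.B, item 10 has two sentences that do different work. The first excludes people: "Pregnant women, nursing mothers, men or women of reproductive ability who are unwilling to use effective contraception or abstinence". The second sets the test: "Women of childbearing potential must have a negative pregnancy test within 2 - 6 weeks prior to treatment".

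The remaining text on pregnancy and pre-dose assessment is short:

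- Section 13.G lists "Occurrence of pregnancy" as a reason to leave the study and gives no test schedule.
- Section 12.A names the routine laboratory work: "A comprehensive chemistry panel, and a complete blood count at each planned visit including the pre-treatment visit, prior to Avelumab infusion".
- Section 12.C says that "patients will undergo a history and physical and, or laboratory evaluations (comprehensive chemistry panel and complete blood count) immediately prior to Avelumab infusion".
- In both Appendix B schedules the pre-treatment row, labelled "Evaluation for treatment", and the Day 0 row include history and physical examination, chemistry, blood count and research blood. Neither schedule has a pregnancy-test column.

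Item 10 does not define treatment. Section 12.C supplies a natural starting point: "The period of monitoring for treatment-related toxicity will start with the first Avelumab infusion".

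**The concern.** The purpose of the test is to find a pregnancy that the patient does not know about before she is exposed to avelumab, and then to radiation or intralesional interferon 7 to 10 days after an infusion. A negative result speaks only for the day of the test. The longer the gap to the first dose, the more room there is for a pregnancy to begin, or to become detectable, without the required test showing it.

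The window in item 10 is long for that purpose. Its lower figure also points the wrong way, because it appears to prefer an older test to a recent one. What is at stake is avoidable fetal exposure in a small number of patients. No estimate or error rate in the trial depends on it.

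**Working it through.** The plan states no figure to reproduce, so the check is calendar arithmetic and a comparison of sections.

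**Inputs**

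- Test window: 2 to 6 weeks before treatment (7.B, item 10).
- Start of treatment: taken as the first avelumab infusion, Day 0 (12.C and Appendix B). This is an assumption, since item 10 does not define it.
- Planned enrolment: 9 women among 20 patients (Section 14).

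**Age of the accepted test at first dose**

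- Upper limit: 6 × 7 = 42 days.
- Lower limit, read literally: 2 × 7 = 14 days. Accepted ages are then 14 to 42 days, and tests aged 0 to 13 days fall outside.
- Lower limit, read loosely as a maximum only: accepted ages are 0 to 42 days.

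The maximum is 42 days on both readings. Only the exclusion of recent tests depends on the literal one.

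**Is the lower bound intended?** Items 3, 4 and 7 of Section 7.A also use six weeks, but with no minimum. Item 3, for example, reads: "If an accessible lesion is present, a biopsy will be performed within 6 weeks of the start of study intervention". A minimum age for a pregnancy test serves no stated purpose, so a drafting slip is the likelier explanation.

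**Is 42 days in keeping with the rest of the plan?** It matches the six-week limit in 7.A, items 3, 4 and 7. Those items concern biopsy, antibody confirmation and measurable disease. The plan is tighter for some other findings that can change:

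- 7.B, item 1 looks at fever in the 72 hours before treatment.
- 7.B, item 8 asks for repeat imaging of small brain lesions once the last scan is more than 4 weeks old.
- Section 11 requires the first avelumab infusion within 4 weeks of the baseline staging scans, that is 4 × 7 = 28 days.

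The accepted pregnancy test may therefore be up to 42 − 28 = 14 days older than the oldest permitted staging scan.

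**Does anything else shorten the gap?** Sections 12.A and 12.C name chemistry and blood count only. Section 13.G acts once a pregnancy is known. History and examination on Day 0 may raise suspicion, but they are not a test. In the text available, item 10 alone fixes the timing.

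**How many patients?** Women make up 9/20 = 45% of planned enrolment. Section 3.A lists age over 50 as a risk factor, while Section 7.A admits patients from age 18. The documents do not say how many women would be of childbearing potential. Nine is a planned number of women and not a cap, so it does not bound the number affected.

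**The case against.** Four arguments on the other side deserve weight.

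**Pregnant women are already excluded.** This stands, and it limits the point. A reader might infer that item 10 makes a pregnant woman eligible if her test is old enough. It does not. She would satisfy the test sentence only, and a later positive result would still exclude her under the first sentence. The gap concerns a pregnancy that nobody has recognised.

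**The lower bound is a slip, and no site would refuse a recent test.** Probably so. A reader might infer that the protocol forbids testing in the last 13 days. Nothing in it does; the sentence only fails, on a literal reading, to count such a test. The substance lies in the 42-day limit, which does not need that reading.

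**A test may be required elsewhere.** Some pages of the document were not available, and the plan refers to an MOP and an Investigator's Brochure that were not seen. The conclusion is therefore confined to the text at hand. Nor does the silence of Appendix B show that the test was forgotten: the appendix is not a full list of eligibility tests, and it lets standard-of-care results be used for eligibility.

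**Any shorter window is a preference.** The documents supply no alternative figure, so 14 days is only an example. That leaves the length open. It does not show that 42 days is suitable for a status that can change within that time.

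**Conclusion.** The point holds and is minor. With treatment taken to start at the first avelumab infusion, item 10 accepts a negative pregnancy test up to 42 days old, and the available text requires no later one. A patient whose pregnancy began or became detectable in the interval could be dosed without the required test having shown it. The contraception requirement, the separate exclusion of pregnant women and the Day 0 examination lower that risk but do not replace a recent test.

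The number affected is not given and is likely to be small. The documents do not show that any enrolled patient would in fact be affected. The literal 2-week floor is a wording fault to correct at the same time; it is not evidence of a deliberate bar on recent tests.

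**What to change.** Delete the 2-week lower bound and tie the window to the first dose. Possible wording: *For women who could become pregnant, a pregnancy test done in the 14 days before the first avelumab infusion must be negative, with the result known before dosing.* The 14 days is an example, and a shorter window would serve equally well; the sponsor should choose the length.

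The pre-treatment row of Appendix B carries no date, and the baseline scans may precede avelumab by up to 4 weeks, so a test at that visit could fall outside a 14-day window. In that case, run the test on the blood draw already scheduled for Day 0 and hold the infusion until the result is back.

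The cost is a re-dated or repeated pregnancy test for the few women of childbearing potential. With the Day 0 draw available, no extra visit is needed. Sample size and analysis are unchanged.

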8. CONSENTING

Prior to consenting to this study, patients will have been HLA typed. If they express an HLA type for which T cells can be generated (HLA A*0201, HLA A*2402 or HLA B*3502), they will have undergone a leukapheresis under protocols **2365** (see **Section 10.A.1**). Thus: at the time of the consent, they will already be designated for Group 1 or 2. An enrollment conference will be held with the patient. The PI or a delegated representative will discuss this study and alternative treatments available for metastatic MCC. All known risks and potential hazards of treatment with IFN β -IB, radiation and PD-L1 and MCPyV-specific CD8 $^{+}$ T polyclonal cells (Group 2) will be discussed. Informed consent will be obtained from the patient using forms approved by the Institutional Review Board (IRB) of the FHCRC. The patient will also be informed that they may withdraw from the study at any time and for any reason without jeopardizing their future treatment. Patients who are designated for treatment on Group 2 will also be informed that they will receive alternative treatment on Group 1 in the unlikely case that MCPyV-specific T-cells cannot be generated for them. In accordance with federal regulations (21 CFR 312), the patient must sign the IRB-approved consent form in the presence of a witness.

